11.6 Transfusion related acute lung injury (TRALI)

Patients meet the TRALI outcome if they have a clinically diagnosed TRALI between initiation of the study product and hospital discharge.

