5. STUDY INTERVENTIONS

5.1 Treatment of Study Participants

A summary of the trial's schedule of events is included in Appendix A.

Timing of study procedures is based on the time of initiation of the study product infusion, which is defined as "Time 0". Study Day 1 is defined as the calendar day of study product infusion. For patients who are randomized but do not receive study product, time of randomization will be considered "Time 0" and Study 1 will be the calendar day of randomization. For most patients, randomization and study product infusion will occur on the same day; in the event the study product is infused on a different calendar day than randomization, Study Day 1 is defined as the day on which study product is infused. "Baseline status" represents the patient's status immediately prior to study infusion, and baseline variables should represent information available before and as close as possible to initiation of the study infusion. The primary outcome will be assessed on Study Day 15 which corresponds to 2 weeks (14 days) after the receipt of the study infusion.

Transfusion of convalescent plasma or placebo will be administered as a single dose by clinical or research personnel while the patient is hospitalized and within 24 hours of randomization. Participants randomized to active treatment will receive 1 unit of convalescent plasma, which has a volume of 200-399 ml infused intravenously. Patients randomized to placebo will receive 250 ml of lactated Ringer's with multivitamin additives infused intravenously. The duration of infusion is recommended to be between approximately 1 hour and 3 hours (at the discretion of the provider), with the specific rate of infusion determined by the site investigator based on an assessment of how quickly the participant can safely receive the intravascular volume load.

Study personnel will monitor patients for adverse reactions to the transfusion while the patient is in the hospital for 72 hours following the infusion; that is transfusion adverse reaction monitoring will be continued until Study

Day 4. For patients who are discharged prior to Day 4, study personnel will obtain safety outcomes from the patient or surrogate via telephone follow-up scheduled at Day 8. Research personnel will also assess patients at Day 15 and Day 29; these assessments will be completed by phone if the patient has been discharged from the hospital.

Screening, consent, and baseline

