5.4 Co-interventions

Use of open label convalescent plasma in the first 15 days of the study is strongly discouraged and will be tracked as protocol deviations. All other treatment decisions will be made by treating clinicians without influence from the protocol. Administration of other antiviral medications will be allowed. The decision to administer other antiviral medications will be made by treating clinicians and will be recorded in the case report form. The decision to administer immunomodulating medications, including corticosteroids, will be made by treating clinicians and will be recorded in the case report form.

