6.4 Outcomes with a competing risk of death

Some secondary outcomes, like the primary outcome, incorporate death as part of the scale. Others, such as length of hospital stay, do not. Because death censors length of stay, it is a competing outcome. Outcomes with a competing risk of death will be analyzed with a multi-state model. Both the instantaneous risk and cumulative risk of the outcome will be reported.

7 Safety Outcomes and Adverse Events

The frequency and description of safety outcomes and adverse events will be reported for all enrolled patients grouped by treatment assignment. The association between treatment received and safety

outcomes between groups will be estimated without covariate adjustment. The following table lists the safety outcomes and the planned analyses.

Outcome	Type	Analysis
Receipt of renal replacement therapy	Binary	Risk difference
Documented venous thromboembolic disease (DVT or PE)	Binary	Risk difference
Documented cardiovascular event (myocardial infarction or ischemic stroke)	Binary	Risk difference
Transfusion reaction	Binary	Risk difference
Transfusion related acute lung injury (TRALI)	Binary	Risk difference
Transfusion associated circulatory overload (TACO)	Binary	Risk difference
Transfusion related infection	Binary	Risk difference

8 Definition of the Primary Outcome

The primary outcome is patients' clinical status 14 days after randomization (measured on Study Day 15) as assessed with the seven-category COVID Ordinal Outcome Scale:

- Not hospitalized without limitation in activity
- Not hospitalized with limitation in activity
- Hospitalized not on supplemental oxygen
- Hospitalized on supplemental oxygen
- Hospitalized on non-invasive ventilation or high-flow nasal cannula
- Hospitalized on invasive mechanical ventilation or extracorporeal membrane oxygenation
- Death

While patients are in the hospital, primary outcome assessment will be performed by review of the electronic health records. For patients discharged prior to 14 days after randomization, study staff will call patients or their surrogates to obtain the patients' clinical status for primary outcome assignment.

9 Definition of SOFA Score

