11.5 Transfusion reaction

Patients meeting any of the following within 6 hours of initiation of the study product infusion will be classified as experiencing symptoms consistent with a transfusion reaction:

- New increase in body temperature, defined as temperature >38.0 C (100.4 F) or increase in temperature by >1 C (1.8 F) compared to temperature at the beginning of the infusion

- Decline in oxygen saturation, defined as an absolute drop in SpO₂ by more than 4% or increase in supplemental oxygen to prevent an absolute drop in SpO₂ by more than 4%
- New hives
- New rash (other than hives)
- New itching
- Chest imaging, such as a chest x-ray, demonstrating new or worsening pulmonary edema, pulmonary infiltrates, or effusion
- Clinically diagnosed anaphylaxis

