11.7 Transfusion associated circulatory overload (TACO)

Patients meet the TACO outcome if they have a clinically diagnosed TACO between initiation of the study product and hospital discharge.

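### The SAP counts TRALI and TACO to hospital discharge with no link to the study infusion, which adds background cases to both arms and costs precision in the risk difference.

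*SAP*

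**What the plan says.** SAP 11.6: "Patients meet the TRALI outcome if they have a clinically diagnosed TRALI between initiation of the study product and hospital discharge". SAP 11.7: "Patients meet the TACO outcome if they have a clinically diagnosed TACO between initiation of the study product and hospital discharge". Each definition has two conditions, a clinical diagnosis and a time window. Neither asks whether the study infusion was the cause.

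Other parts of the plan stay closer to the infusion:

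- SAP 11.5 counts a transfusion reaction only "within 6 hours of initiation of the study product infusion".
- Protocol 5.1 provides for 72 hours of in-hospital observation: "transfusion adverse reaction monitoring will be continued until Study" Day 4.

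Later transfusion is open. Protocol 5.4 states: "Use of open label convalescent plasma in the first 15 days of the study is strongly discouraged and will be tracked as protocol deviations". It leaves every other treatment decision to the treating clinicians. Among blood products, Protocol 7.2 lists only open-label convalescent plasma for recording.

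SAP 7 and Protocol 8.7 (Table 3) analyse TRALI and TACO as separate binary outcomes, each by an unadjusted risk difference.

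**The concern.** Protocol 10.1.1 names TRALI and TACO as risks of plasma, and the risk-difference rows are where the trial will report them. The counting window can run for weeks beyond the 72 hours in which infusion reactions are monitored. In that time a patient in either arm may receive red cells, platelets, ordinary plasma or open-label convalescent plasma. A reaction to any of these meets the definition as written.

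Two things are at stake. First, for rare outcomes even a small background makes the risk difference noticeably less precise. Second, the plasma-arm percentage mixes reactions to the study unit with reactions to other products, so it cannot be read as the risk of the study unit. The data items listed in the protocol would not allow the two to be separated afterwards, except for open-label convalescent plasma.

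**Working it through.** The documents state no rate, power or precision for TRALI or TACO, so there is no figure of the plan's own to reproduce. The calculation below shows how the counting rule behaves under assumed rates.

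**Inputs**
- n = 500 per arm (SAP 4).
- Effect measure: unadjusted risk difference (SAP 7; Protocol Table 3).
- p = risk caused by the study plasma; assumed 2%.
- b = risk of a counted case from a later transfusion; assumed 0 to 1%, equal in both arms.

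**Formulas**
- Plasma arm: pT = 1 − (1 − p)(1 − b). Control arm: pC = b.
- Risk difference: RD = pT − pC = p(1 − b).
- SE = √[pT(1 − pT)/n + pC(1 − pC)/n].

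For b = 1%: pT = 1 − 0.98 × 0.99 = 0.0298, and SE = √(0.0298 × 0.9702/500 + 0.01 × 0.99/500) = √(0.0000578 + 0.0000198) = 0.0088.

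| Background b | pT | pC | RD (points) | SE (points) |
|---|---|---|---|---|
| 0 | 2.00% | 0 | 2.00 | 0.63 |
| 0.2% | 2.20% | 0.2% | 2.00 | 0.69 |
| 0.5% | 2.49% | 0.5% | 1.99 | 0.76 |
| 1% | 2.98% | 1% | 1.98 | 0.88 |

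(At 0.5%, simply adding the two risks, 2.5% against 0.5%, gives an SE of 0.77.)

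The difference is almost unchanged. The half-width of a 95% interval grows from about 1.2 points (1.96 × 0.63) to about 1.7 (1.96 × 0.88). The plasma-arm percentage reads 2.98% when the study unit causes 2%.

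**How large might b be?** If 20% of patients received another product and 2.5% to 5% of those reacted, b = 0.20 × 0.025 to 0.20 × 0.05 = 0.5% to 1%. If 5% received one and 2% reacted, b = 0.05 × 0.02 = 0.1% and the SE is 0.66. All these rates are assumptions.

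**When does bias appear?** Take p = 1% and a plasma-arm background of 1%, so pT = 1.99%. With control background 1%, RD = 0.99 points. With 1.5% it is 0.49, and with 2% it is −0.01. Unequal background can therefore erase the difference. It could arise if one arm is transfused more later on, or if one arm stays in hospital longer and so has a longer counting window.

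**The case against.** The case for leaving the rule alone is a good one.

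- **The comparison is randomised.** Equal background is subtracted out. This stands. A reader might infer that the plasma effect is hidden or pulled toward zero. With equal background it is not, and nothing in the documents shows unequal background.
- **No test is planned.** A reader might put the harm as lost power in a significance test. The plan specifies no test or power for these outcomes, so the standard error is the appropriate measure.
- **Placebo-arm cases may be genuine comparators.** A reader might infer that every TRALI or TACO on lactated Ringer's must come from another product. Protocol 10.1.2 lists volume overload as a risk of the placebo infusion, so a TACO diagnosis there need not.
- **Open-label plasma in controls.** It is tempting to say such cases are counted against placebo. SAP 7 refers to treatment received and Protocol 8.7 to intervention group, so the documents do not settle this.
- **Attribution exists elsewhere.** Investigators grade relatedness (Appendix B.2) and the medical monitor makes the final attribution (Protocol 12.4). Study-related cases must be reported as adverse events. This mitigates the problem, but neither the SAP definitions nor the risk-difference rows use that attribution.
- **The manual of operations is not available.** Protocol 7.2 says it describes the variables for site staff, and it may add a restriction. The same sentence places the definitions in the SAP, which has none.
- **Counting to discharge is inclusive** and matches the end of the window in SAP 11.2 to 11.4. That is a reason to keep this count as a supplementary row. It does not make it the best measure of harm from one infusion.

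**Conclusion.** The point holds as a loosely stated counting rule with a modest, avoidable cost. SAP 11.6 and 11.7 admit cases unrelated to the study infusion over a window much longer than the one Protocol 5.1 monitors. With equal background the risk difference stays nearly unbiased (2.00 against 1.98 points at 1% background), while its standard error rises from 0.63 to between 0.69 and 0.88 points as background goes from 0.2% to 1%. The plasma-arm risk is not the risk of the study unit.

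These sizes rest on 500 per arm, an assumed 2% plasma-caused risk and assumed background rates. With the background near 0.1% the loss would be slight. Bias needs a difference between arms in later transfusion or time to discharge, which is possible but not shown. The primary endpoint is unaffected.

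**What to change.** In SAP 11.6 and 11.7, base the risk difference on cases with onset within the 72 hours after study infusion that Protocol 5.1 already monitors, applied identically in both arms. Report all cases to discharge, by arm, as a supplementary row.

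Do not exclude a case because another blood product was given before onset. That would condition on an event after randomisation and could discard true reactions to study plasma. Instead, record any intervening product and the medical monitor's attribution for each case, and list them by arm.

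The cost is a change of SAP wording plus, for the few diagnosed cases, onset date and time, any intervening product and the attribution. The downside is that a study-plasma case with onset after 72 hours appears only in the supplementary row. Some background within the 72 hours will remain. The change concerns counting only and alters no patient care.

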11.7 Transfusion associated circulatory overload (TACO)

Patients meet the TACO outcome if they have a clinically diagnosed TACO between initiation of the study product and hospital discharge.

